## 2. Maintenance monotherapy period

Duration, total number of days, average daily dose, and DI of veliparib/placebo as described above will be summarized by descriptive statistics for veliparib/placebo in maintenance monotherapy.

The actual total dose (ATD), planned total dose (PTD), and dose intensity (DI) for veliparib/placebo in the maintenance monotherapy period is presented in the [Table 4](#).

**Table 4. Definition of Actual Total Dose, Planned Total Dose, And Dose Intensity for Veliparib/Placebo in Maintenance Period**

	ATD (Actual Total Dose)	PTD (Planned Total Dose)	DI (Dose Intensity)
veliparib/placebo	Actual total dose (mg)	800 mg* duration of maintenance therapies	100*ATD/PTD

Duration of maintenance therapy is calculated by subtracting the start date of maintenance therapy from the end date of maintenance therapy plus 1.

## 3. Dose reduction, delay, and interruption,

The numbers and percentages of subjects having dose reduction or interruption or delay for each study drug will be summarized for each treatment arm prior to maintenance monotherapy period. If a subject has any dose reduction from the previous dose of a certain drug, this subject will be considered as having experienced dose reduction of this drug. If the difference between the first dose dates of two adjacent cycles of a certain

drug is more than 21 days, the subject will be considered as having experienced a dose delay of this drug. If a subject skips one or more consecutive dosing days of any drug within a cycle, then this subject is considered as having dose interruption of this drug.

## **10.0 Efficacy Analysis**

### **10.1 General considerations**

Unless otherwise noted, for all statistical analyses, statistical significance will be determined by a one-sided P value  $\leq 0.1$  (when rounded to two decimal places). Confidence intervals will be two-sided 80% for all descriptive statistics. The date of randomization is defined as the date that the IRT issued a subject number.

The efficacy analyses will be performed on Phase 2 ITT population and presented by treatment arm. All randomized subjects will be included unless otherwise specified. The dosing schedules for each of the three arms are listed in detail in Section 4.2.

After observing 95 PFS events (75% of 126), a model-based prediction was performed to estimate the approximate date of the 126th PFS events across all 3 arms. The prediction estimated Sep. 14th, 2018 as the date of 126 PFS events across the three arms. Unless otherwise specified, Sep. 14th, 2018 will be the cutoff date for all efficacy analyses.

For all efficacy endpoints except OS, if a subject's blind has prematurely broken by sites before cutoff date, the date of premature blind break will be set as the cutoff date for that subject.

If a subject starts any systemic anti-cancer therapy post-discontinuation of study therapy, then PFS and DOR will be censored at last non-missing tumor assessment prior to the initiation date of the new systemic anti-cancer therapy; similarly ORR/DOR will be based only on tumor assessment prior to the initiation of any new systemic anti-cancer therapy.

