### 5.3.1.1 Study Procedures

Unless otherwise stated, the baseline measurement for any given variable will be defined as the last value obtained for the variable prior to the first dose of study drug.

The study procedures outlined in [Table 7](#) and [Table 8](#) are discussed in detail in this section, with the exception of the monitoring of treatment compliance (discussed in [Section 5.5.7](#)) and adverse event information (discussed in [Section 6.0](#)). All study data will be recorded on eCRFs with supporting source documentation.

Screening procedures should be performed within 28 days prior to Cycle 1 Day -2. If the screening visit is performed greater than 7 days prior to Cycle 1 Day -2, the physical exam, laboratory tests, and pregnancy test (for female subjects of childbearing potential) must be repeated on Cycle 1 Day -2. Vital signs and performance status assessments will be performed on Cycle 1 Day -2 for all subjects. Baseline radiographic tumor assessments per computed tomography (CT) with IV contrast/magnetic resonance imaging (MRI) of the chest, abdomen, pelvis and head (if CNS metastases are suspected) will be conducted within 21 days prior to Cycle 1 Day -2. If the subject is unable to undergo a CT scan with IV contrast due to allergy or renal insufficiency, a non-contrast CT may be performed. Magnetic resonance imaging (MRI) can be conducted in cases where local laws/requirements mandate, but should have Sponsor approval prior to performing the MRI.

For procedures performed at Screening and repeated, the later procedure performed prior to dosing will serve as a baseline for clinical assessment. Subsequent study procedures should be performed approximately within  $\pm 1$  day on days of IV infusion of carboplatin and etoposide and  $\pm 2$  days for all safety visits and first Maintenance visit. Clinical laboratory tests can be performed up to 48 hours prior to dosing.

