### **Randomization and Subject Number Assignment**

An Interactive Response Technology System (IRT) will be utilized to register subjects.

The site will access the IRT system at Screening, after the subject signs informed consent and a unique subject number will be provided. Subjects who complete all Screening

procedures and meet the eligibility criteria will proceed to dosing. Subjects who sign consent and do not meet the eligibility criteria will be considered a screen failure and the reason for screen failure will be documented in the source and in the eCRF. Subjects will also be registered as a screen failure in the IRT system.

Subjects in Phase 2 who complete all Screening procedures and meet the eligibility criteria will be randomized in a 1:1:1 ratio to one of three treatment arms:

Arm A: veliparib 240 mg in combination with carboplatin/etoposide followed by veliparib 400 mg BID monotherapy

Arm B: veliparib 240 mg in combination with carboplatin/etoposide followed by placebo monotherapy

Arm C: placebo in combination with carboplatin/etoposide followed by placebo monotherapy

A bottle number randomization schedule and a subject randomization schedule will be generated by the Data and Statistical Science Department at AbbVie prior to the start of the study. A copy of all randomization schedules will be kept by the Data and Statistical Science Department at AbbVie and a copy will be forwarded to the IRT vendor.

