#### **5.5.4 Method of Assigning Subjects to Treatment Groups (Phase 2 Randomized Double-Blind)**

All subjects will be randomized using an IRT system. Before the study is initiated, the IRT user manual, which provides instruction on how to use the system via the web or phone, will be provided to each site.

Subjects who complete all Screening procedures and meet eligibility criteria may proceed to randomization. Subject randomization will be stratified by: LDH ( $\leq$  ULN versus  $>$  ULN), and gender; therefore a subject's baseline LDH value must be known prior to randomization and when accessing the IRT to perform the randomization transaction.

The site will contact the IRT to obtain a Screening (subject) number once the subject has signed the informed consent and a study-specific procedure has been performed (i.e., central laboratory samples drawn). Once the subject number is assigned, if the subject is not enrolled/randomized the reason for screen failure will be documented in the source document and in the eCRF. If the subject meets all inclusion and none of the

exclusion criteria, the site will access the system to randomize the subject. The IRT will randomize subjects in a 1:1:1 ratio to one of the three treatment arms as follows:

- Arm A: veliparib in combination with carboplatin/etoposide followed by veliparib monotherapy
- Arm B: veliparib in combination with carboplatin/etoposide followed by placebo monotherapy
- Arm C: placebo in combination with carboplatin/etoposide followed by placebo monotherapy

Subject randomization will be stratified by: LDH ( $\leq$  ULN versus  $>$  ULN), and gender

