## **8.0 Statistical Methods and Determination of Sample Size**

### **8.1 Statistical and Analysis Plans**

For subjects in the Phase 1 portion, the date of enrollment is defined as the first day of study drug administration. For subjects in the randomized Phase 2 portion, the date of randomization (enrollment) is defined as the date that the IRT issued a subject number.

ORR will be performed on all dosed subjects in the Phase 1 portion of the study.

The primary, secondary, and tertiary efficacy analyses will be performed on all subjects in the randomized Phase 2 portion of the study.

Safety analyses will be performed separately for the Phase 1 and Phase 2 portions. All subjects who receive at least one dose of the study drug will be included in the safety analysis.

Unless otherwise noted, data will be summarized for Phase 1 and Phase 2 subjects separately.

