## **8.3 Randomization Methods**

All subjects in the Phase 2 portion of the study will be randomized using an IRT system. Before the study is initiated, directions for the IRT will be provided to each site. The site will contact the IRT to obtain a Screening (subject) number once the subject has signed the informed consent and a study-specific procedure has been performed (i.e., central laboratory samples drawn). Once the Screening number is assigned, if the subject is not randomized into the study, the reason for screen failure will be documented in the source document and in the eCRF. For others, the site will access the system and a unique randomization number will be provided.

The IRT will randomize subjects in a 1:1:1 ratio to one of the treatment arms as follows:

- Arm A: veliparib in combination with carboplatin/etoposide followed by veliparib monotherapy
- Arm B: veliparib in combination with carboplatin/etoposide followed by placebo monotherapy
- Arm C: placebo in combination with carboplatin/etoposide followed by placebo monotherapy

Subject randomization will be stratified by baseline LDH ( $\leq$  ULN versus  $>$  ULN) and gender. The stratification factors used for the randomization should be the last values on or prior to the date of randomization and should be consistent with those on the eCRF.

A bottle number randomization schedule and a subject randomization schedule will be generated by the Clinical Statistics Department at AbbVie prior to the start of the study. A copy of all randomization schedules will be kept by the Clinical Statistics Department at AbbVie and a copy will be forwarded to the IRT vendor.

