## **5.0 Analysis Populations**

### **5.1 Definition for Analysis Population**

Two study populations will be analyzed, respectively defined as follows:

Intent-To-Treat (ITT) population – all subjects who were randomized using an IRT (interactive response technology) system. The data from ITT population will be analyzed by the treatment group assignment given at the time of randomization, even if the subject takes the incorrect drugs that do not match the assigned treatment, or does not receive any treatment, or does not follow the protocol until completion.

As-Treated (AST) population – all subjects who were randomized by IRT system and took at least 1 dose of study drug (veliparib/placebo). The data from AST population will be analyzed by the actual treatment that subject received.

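### The randomization date, time zero for PFS and OS, is tied to the IRT subject number, which is issued at Screening

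*SAP*

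**What the plan says.** SAP 10.1, and SAP 6.0 in the same words, state: "The date of randomization is defined as the date that the IRT issued a subject number". Protocol 8.1 says the same for Phase 2: "the date of randomization (enrollment) is defined as the date that the IRT issued a subject number". SAP 10.3 counts both PFS and OS from the date of randomization, and SAP 10.4.1 reports median PFS and PFS rates at Months 3 and 6.

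The protocol's operational sections place the subject number at a different event:

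- Section 5.3.1.1 (Randomization and Subject Number Assignment): "The site will access the IRT system at Screening, after the subject signs informed consent and a unique subject number will be provided".
- Section 5.5.4: "The site will contact the IRT to obtain a Screening (subject) number once the subject has signed the informed consent", with a study-specific procedure also done. The same section covers people who hold a number but never enter the trial: "Once the subject number is assigned, if the subject is not enrolled/randomized the reason for screen failure will be documented".
- Section 8.3 describes a later step for those who do enter: "the site will access the system and a unique randomization number will be provided".
- Table 8 marks Randomization at Cycle 1 Day −2, and Section 5.5.4 requires the baseline LDH result before randomization.
- Section 5.3.1.1 sets the screening window: "Screening procedures should be performed within 28 days prior to Cycle 1" (Day −2).

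**The concern.** The subject number and the randomization number come from two separate IRT transactions on potentially different dates, and the analysis definition names the first. Between them come eligibility confirmation and the LDH result, so a gap should be expected for many subjects.

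A subject must survive that gap to be randomized, and no progression can be recorded in it. It is therefore event-free by construction. If it is counted, the Kaplan-Meier curves for PFS and OS shift to the right in every arm. The prespecified medians and the Month 3 and Month 6 PFS rates would then be too high. The date also serves as the baseline anchor for untreated subjects (SAP 6.0) and as the limit for stratification values (SAP 4.2, Protocol 8.3).

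**Working it through.** **Inputs.** Arm C median PFS 5.5 months; hazard ratio 0.63 for A versus C; 85 events in A and C combined; one-sided alpha 0.1; 60 subjects per arm (SAP 4.3, Protocol 8.2). Screening window 28 days (Protocol 5.3.1.1). The actual gap is not given, so 7, 14 and 28 days are assumed. A month is taken as 30.4375 days, giving gaps g of 0.230, 0.460 and 0.920 months.

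**Step 1: the plan's own figure.** Schoenfeld's formula gives 4 × (1.2816 + 0.8416)² / (ln 0.63)² = 18.03 / 0.2135 = 84.5, so 85 events. Power at 85 events is Φ(√85/2 × 0.4620 − 1.2816) = Φ(0.848) = 80.2%. With uniform accrual over 6 to 24 months (assumed), the three-arm total when A and C reach 85 is 126.4 to 126.7. Both figures in the plan reproduce.

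**Step 2: moving time zero back.** Under exponential PFS with a constant gap g:

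- reported median = true median + g
- reported PFS rate at month t = exp(−ln 2 × (t − g) / true median)

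The Arm A median is 5.5 / 0.63 = 8.73 months. Example, Arm C at Month 3 with 14 days: exp(−0.6931 × 2.540 / 5.5) = exp(−0.320) = 72.6%.

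| Gap (days) | Median C | Median A | Month 3 C | Month 3 A | A − C (points) | Month 6 C | Month 6 A | A − C (points) |
|---|---|---|---|---|---|---|---|---|
| 0 | 5.50 | 8.73 | 68.5% | 78.8% | 10.3 | 46.9% | 62.1% | 15.2 |
| 7 | 5.73 | 8.96 | 70.5% | 80.3% | 9.7 | 48.3% | 63.2% | 14.9 |
| 14 | 5.96 | 9.19 | 72.6% | 81.7% | 9.1 | 49.7% | 64.4% | 14.7 |
| 28 | 6.42 | 9.65 | 76.9% | 84.8% | 7.8 | 52.7% | 66.8% | 14.1 |

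The Arm C median rises by 0.23/5.5 = 4%, 0.46/5.5 = 8% and 0.92/5.5 = 17%. The A − C difference in medians stays at 3.2 months. If the gap instead varies uniformly over 0 to 28 days, the Arm C results are close to the 14-day row: median 5.96 months, Month 3 72.65%, Month 6 49.8%.

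**Step 3: the test and the hazard ratio.** Adding the same number of days to every subject leaves the risk sets unchanged, so a constant gap leaves the log-rank statistic and the hazard ratio exactly as they were. A variable gap was simulated: 3,000 trials per scenario, 60 versus 60, cutoff at the 85th event, 15-month accrual (assumed), unstratified log-rank, gap uniform on 0 to 28 days and independent of arm.

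| Quantity | Correct time zero | With gap |
|---|---|---|
| Power, continuous times | 79.5% | 79.3% |
| Power, 6/9-week scan grid | 79.1% | 78.8% |
| Type I error, continuous | 10.4% | 10.2% |
| Type I error, scan grid | 10.1% | 10.4% |
| Mean HR, continuous | 0.631 | 0.631 |
| Mean HR, scan grid | 0.634 | 0.633 |

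The significance call differed in 1% to 2% of trials, with no systematic direction. Event counts and the calendar cutoff do not depend on time zero.

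**The case against.** The strongest reply is that the intended meaning is plain and nobody would program the sentence literally. SAP 5.1 analyzes subjects "by the treatment group assignment given at the time of randomization". The LDH stratifier has to be known before randomization, yet the subject number is issued once samples are merely drawn. SAP 8.0 counts screen failures apart from randomized subjects, and Table 8 puts randomization at Cycle 1 Day −2. On that view this is a terminology error with no inferential effect.

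Much of this stands. The wording is probably a slip, and the primary test, the hazard ratio and the testing hierarchy are not at risk. Nor does either document plan a formal comparison of the observed median with 5.5 months.

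Two things do not follow. First, context makes the intention likely but does not change the rule: the sentence appears three times, the subject number is a real IRT output with its own date, and SAP 3.0 says the document guides the programming. Second, descriptive does not mean unimportant, since the medians and Month 3 and Month 6 rates are prespecified outputs.

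The 28-day figure is also open to challenge. The window limits screening procedures before Day −2; it does not directly limit the time from subject number to randomization. Section 5.3.1.1 ties the number to consent, for which no limit is stated. The 28-day row is therefore an extreme case, requiring that gap in every subject. A four-day limit on obtaining the number appears only in superseded text in Appendix G and cannot be relied on now.

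**Conclusion.** The point holds: the definition names the wrong IRT transaction, and no current passage corrects it. If followed, it would raise median PFS in each arm by the gap itself, 0.23 to 0.92 months for gaps of 7 to 28 days. Month 3 PFS would rise by up to 8.4 points in Arm C and 6.0 in Arm A, and Month 6 PFS by up to 5.8 and 4.7 points. Each subject's OS time would lengthen by the same number of days.

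These sizes assume exponential PFS at the planning values and a gap the documents do not report. The effect is zero for any subject numbered on the day of randomization. There is no material effect on the primary comparison. This should be fixed because it is the time-zero rule for the primary endpoint, but it does not threaten the trial's main inference.

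**What to change.** In SAP 6.0 and 10.1, define the date of randomization as the date of the IRT randomization transaction, when the randomization number and treatment arm are assigned. State that this date is time zero for PFS and OS, and add a matching clarification to Protocol 8.1.

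As a separate small addition, SAP 10.3 should say from which date its Day 168 and Day 210 limits for missed assessments are counted. Scans are scheduled from Cycle 1 Day −2, so the origin should be consistent with that.

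The cost is one sentence in each of two SAP sections, one clause in SAP 10.3 and one clarification line for the protocol. The documents do not say whether the IRT randomization date is transferred to the analysis data; confirm this before programming.

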**Table 8. Study Activities in Phase 2 (Continued)**

- a. Screening visit must be performed within 28 days of Cycle 1 Day -2. If the screening visit is performed > 7 days prior to Day -2 the physical exam, laboratory tests (hematology and chemistry) and pregnancy test must be repeated on Cycle 1 Day -2. Tumor assessments must be performed within 21 Days of Cycle 1 Day -2.
- b. The informed consent must be signed and dated prior to the initiation of any screening or study specific procedure being performed.
- c. A subject's medical history will be reviewed at each visit. Any changes from baseline will be recorded on the adverse event eCRF.
- d. Physical exam does not need to be repeated at Cycle 1 Day -2 if screening physical exam was completed within 7 days of Cycle 1 Day -2. Physical exams during combination cycles must include assessment of hearing if required by the local SmPC for carboplatin. The Cycle 1 Day 8 physical exam may be symptom directed. Height will be assessed at Screening only.
- e. A serum pregnancy test must be performed at Screening, a urine pregnancy test on Cycle 1 Day -2 prior to dosing if > 7 days since obtaining the serum pregnancy test for women of childbearing potential. Pregnancy tests may be repeated at any time during the study at the discretion of the investigator.
- f. Hematology and Chemistry panels do not need to be repeated at Cycle 1 Day -2 if screening labs were completed within 7 days of Cycle 1 Day -2. A central laboratory will be used for the study; however, sites may use a certified local laboratory to collect a sample to dose the subject. If local labs are drawn the sample MUST be split and also sent to central lab.
- g. Only for subjects with known history of HBV or HCV without prior evidence of active disease-free status and if HBsAg/HCV RNA status within 3 months of the study entry is unknown.
- h. If clinical disease progression is suspected, progression must be confirmed radiographically per RECIST 1.1. Clinical disease progression will include, but will not be limited to worsening performance status due to progressive disease, requirement for non-palliative radiation therapy, alternative chemotherapy or surgery due to progressive disease. At the Final Visit, a clinical disease progression assessment is required only for subjects who discontinue the study for reasons other than progression (clinical or radiographic).

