- i. Tumor assessment and assessment of response will occur every 6 weeks ( $\pm$  1 week) from CID-2 for the first 30 weeks, then every 9 weeks ( $\pm$  1 week) thereafter. A tumor assessment will be performed at the Final Visit for subjects who discontinue the study for reasons other than radiographic progression and if no assessment has been performed within the last 4 weeks. An unscheduled assessment should be obtained in such subjects if a Final Visit will not be conducted. Subjects in Post-Treatment Follow-Up should continue to receive tumor assessments at the protocol defined time points until an event of radiographic progression.
- j. Veliparib will be dosed orally at 240 mg BID and 14-day schedule for up to 6 cycles. Veliparib will be administered after the pre medications on all days when given with chemotherapy. Veliparib will be given approximately every 12 hours with a glass of water (approximately 240 mL).
- k. Pre-medication will be given as per institutional guidelines.
- l. Starting at Maintenance Day 1 and all subsequent monotherapy cycles, veliparib or placebo will be dosed orally at 400 mg BID and continuous (21-day) dosing schedule. Subjects should remain on veliparib until disease progression or unacceptable toxicity occurs.

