### **8.1.2 Efficacy Endpoints**

#### **8.1.2.1 Primary Efficacy Endpoint**

The primary efficacy endpoint is progression-free survival (PFS).

Progression-free survival will be defined as the number of days from the date of randomization to the date of earliest disease progression (radiographic progression per RECIST version 1.1) or death. All events of disease progression will be included, regardless of whether the event occurred while the subject was still taking study drug or had previously discontinued study drug. If the subject does not have an event of disease progression nor has the subject died, the subject's data will be censored at the date of the subject's last available radiographic disease progression assessment.

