### 10.3 Definition of Efficacy Endpoints

**PFS (progression-free survival):** the number of days from the date of randomization to the date of earliest radiographic disease progression or death provided no radiographic disease progression occurred.

All events of disease progression before the initiation of anti-cancer post-treatment therapy will be included, regardless of whether the event occurred while the subject was still taking study drug or had previously discontinued study drug. However, if a disease progression event occurs immediately after a subject misses two or more consecutive disease progression assessments (e.g., 84 days = 12 weeks if previous tumor scan were prior to or on Week 24 Day 7 (Day 168), 105 days = 15 weeks if previous tumor scan were in between of Week 25 Day 1 and Week 30 Day 7 (Day 210), and 126 days = 18 weeks if previous tumor scan were on or after Week 31 Day 1), then this subject's data will be censored at the last disease progression assessment prior to the missing disease progression assessments, or at randomization if disease progression occurred at the first post-baseline disease assessment. All events of death before the initiation of anti-cancer post-treatment therapy will be included for subjects (whether had post-baseline tumor assessment or not) who had not experienced disease progression, regardless of whether the event occurred while the subject was still taking study drug or had previously discontinued study drug. Similar to disease progression, if a death event occurs immediately after a subject misses two or more consecutive disease progression assessments (length of gap is calculated the same way as disease progression), then this subject's data will be censored at the last tumor assessment before death, or at randomization provided subject did not have any post-baseline disease assessment.

If a subject did not have an event of disease progression nor has the subject died on or prior to the cutoff of PFS analysis, this subject's data will be censored at the date of his/her last disease assessment or randomization date provided subject did not have any post-baseline disease assessment.

**OS (overall survival):** the number of days from the date of randomization to the date of death. All events of death will be included.

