## **10.8 Additional Efficacy Analysis**

The following additional efficacy analysis may be performed:

1. Modified PFS analysis for Arm A & Arm C to consider the initiation of any anti-cancer post-treatment therapy as an event.
2. Modified ORR analysis for Arm A & Arm C and DOR analysis for all 3 arms where both confirmed and unconfirmed responses are to be considered.

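### The SAP's PFS stops at new systemic anticancer therapy, the Protocol's does not, and no planned analysis estimates the Protocol's primary endpoint

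*SAP*

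**What the plan says.** **Protocol.** Section 8.1.2.1 sets the primary endpoint: "Progression-free survival will be defined as the number of days from the date of randomization to the date of earliest disease progression" (radiographic, by RECIST 1.1) or death. It adds: "All events of disease progression will be included, regardless of whether the event occurred while the subject was still taking study drug", or had already stopped it. Only a subject with neither progression nor death is censored, at the last radiographic assessment. New anticancer therapy is not mentioned, and the synopsis agrees. Follow-up matches this definition. Table 8, footnote i, says: "Subjects in Post-Treatment Follow-Up should continue to receive tumor assessments at the protocol defined time points until an event of radiographic progression". The Post-Treatment Follow-Up paragraphs in 5.3.1.1 and 5.4.1 say the same, and none of these passages stops scanning at next-line treatment.

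**SAP.** Section 10.1 states: "If a subject starts any systemic anti-cancer therapy post-discontinuation of study therapy, then PFS and DOR will be censored at last non-missing tumor assessment", the one preceding the new therapy. Section 10.3 counts progressions only before post-treatment anticancer therapy and applies the same limit to deaths: "All events of death before the initiation of anti-cancer post-treatment therapy will be included for subjects" without earlier progression. Section 6.0 excludes surgery and radiation from post-treatment therapy, so the rule concerns systemic treatment. Two other rules are absent from Protocol 8.1.2.1:
- Section 10.3 censors a progression or death that follows two or more consecutive missed assessments.
- Section 10.1 ends a subject's data at the date of a premature unblinding by the site, for every efficacy endpoint except OS.

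Section 10.4.1, the only primary analysis, uses the SAP definition. The one alternative is item 1 of 10.8, introduced as something that may be done: "Modified PFS analysis for Arm A & Arm C to consider the initiation of any anti-cancer post-treatment therapy as an event".

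**The concern.** The SAP replaces the Protocol's primary endpoint without saying so. It does announce and explain its change to the ORR assessment period (SAP 4.1), so a reader would expect the same for PFS. As planned, the trial would report no estimate of the quantity named in its primary objective, although the design schedules the scans needed for it.

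The substitution may not be neutral. Protocol 5.3.3.2 lists a need for chemotherapy because of progressive disease among the signs of clinical progression, and 5.4.1 says Final Visit procedures should not hold up a new treatment. A subject who worsens between scans can therefore start second-line therapy before a scan confirms progression. The SAP then censors that subject at the previous scan and ignores the later progression or death. Censoring of that kind depends on prognosis. PFS for A vs C also opens the testing sequence in SAP 10.2, so every secondary claim rests on it.

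**Working it through.** **1. The definitions side by side.** Take a subject who stops study drug without radiographic progression, starts systemic therapy, and later progresses on a scheduled scan or dies.
- Protocol 8.1.2.1: event, at the date of progression or death.
- SAP 10.1 and 10.3: censored at the last assessment before the new therapy.
- SAP 10.8, item 1, if run: event at the start of the new therapy.

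These are three different endpoints, and no planned analysis uses the first.

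**2. The plan's own figures** (Protocol 8.2, SAP 4.3: control median 5.5 months, HR 0.63 for A vs C and 0.75 for B vs C, one-sided alpha 0.1, 80% power, 60 per arm).
- Events: d = 4(z₀.₉ + z₀.₈)² / (ln 0.63)² = 4(1.2816 + 0.8416)² / 0.4620² = 84.5, so 85.
- Power: Φ(|ln 0.63|·√d / 2 − 1.2816). At d = 85 this is Φ(0.848) = 80.2%.
- Total: with exponential PFS and assumed uniform accrual over 0 to 24 months, Arm B has 41.4 to 41.7 events when A and C together reach 85. The total is 126.4 to 126.7, against the stated 126.

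The stated design reproduces.

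**3. Power if events are lost and not replaced.** The documents give no rate of new therapy before radiographic progression, so the share lost is an assumption.

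| Share lost | A + C events | Power |
|---|---|---|
| 0% | 85 | 80.2% |
| 5% | 80.8 | 78.7% |
| 10% | 76.5 | 77.0% |
| 15% | 72.2 | 75.2% |
| 20% | 68.0 | 73.4% |

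**4. Illustrative simulation of the hazard ratio.** Assumptions: exponential PFS; 10% or 20% of subjects start new therapy 1.5 months before radiographic progression and are censored at a scan 0 to 1.4 months before that; 18-month cutoff; 200,000 subjects per arm, with the Cox fit on a random 20,000.
- Equal switching: HR 0.632 (10% in each arm) and 0.634 (20% in each arm).
- 10% in A and 20% in C: 0.691. 20% in A and 10% in C: 0.561.
- True HR 1.0 with the same unequal shares: 1.13 and 0.92.
- Control median: about 5.9 months at 10% and 6.6 at 20%, against about 5.5 under the Protocol definition.

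A second simulation used the Protocol scan schedule (weeks 6, 12, 18, 24 and 30, then every 9 weeks). It counted a clinical-first progression at the next scan under the Protocol and censored it at the previous scan under the SAP. It gave 0.62 to 0.63 with equal shares, and 0.69 and 0.57 with unequal shares.

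**The case against.** Censoring at new therapy is a recognised convention, and which rule should be primary is a genuine trade-off. That stands. It does not excuse an undeclared change or the absence of any Protocol-defined analysis.

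A reader might draw stronger conclusions that the documents do not support:
- **That the A vs C hazard ratio is biased.** The shifts to about 0.57 or 0.69 need a twofold difference in switching between arms of a double-blind trial. Nothing in the documents indicates one, and equal switching leaves the ratio unchanged. Subjects who stop for toxicity enter Post-Treatment Follow-Up, and nothing says that they start new therapy.
- **That medians are inflated in every arm.** This holds only if switching marks clinical failure.
- **That power is lost.** The analysis is triggered by events (Protocol 8.1.8), with a cutoff of 14 September 2018 predicted after 95 PFS events (SAP 10.1). If those 95 were counted by the SAP definition, the 126 target already allows for the censoring. The documents do not say which definition was used.
- **That every needed scan will exist.** Protocol 5.3.1.1 lets subjects leave by investigator decision or withdrawal of consent, after which only survival is followed. Later scans are planned, not assured.
- **That the Final Visit scan waiver explains lost events.** Footnote h says: "If clinical disease progression is suspected, progression must be confirmed radiographically per RECIST 1.1". Footnote i asks for a Final Visit scan only "if no assessment has been performed within the last 4 weeks". Four weeks is 28/42 = 67% of a 6-week interval but 28/63 = 44% of a 9-week one, and neither figure is a share of lost events. Subjects who stay on study keep their scheduled scans. The footnotes can be read together; this is a wording matter.

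Item 1 of SAP 10.8 does probe informative censoring for A vs C. Its weaknesses are that it is optional, omits B vs C, and does not estimate the Protocol's endpoint.

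**Conclusion.** The point holds as a conflict of definitions. SAP 10.1 and 10.3 exclude progressions and deaths after new systemic anticancer therapy, and the missed-assessment and unblinding rules depart further from Protocol 8.1.2.1. None of these departures is declared as a change to PFS, and the Protocol's PFS is not analysed anywhere.

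The numerical consequence is unknown. The hazard ratios rest on an assumed 10-20% switching rate, and any material movement also needs unequal switching. The 73-77% power range rests on 10-20% of events being lost and not replaced at the fixed cutoff. These figures show why the definition matters; they do not estimate bias in this trial. The case for change does not depend on them, because the trial should be able to report its own stated primary endpoint.

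**What to change.** - State in SAP 10.3 and 10.4.1 that PFS by Protocol 8.1.2.1 will be analysed for A vs C and B vs C: first radiographic progression or death, regardless of new therapy, missed assessments or premature unblinding. Make it the primary analysis with the SAP censoring as sensitivity, or make it a required sensitivity analysis with the change from the Protocol declared and justified. Either choice reconciles the documents. Removing the new-therapy rule alone would not restore the Protocol definition.
- Make item 1 of SAP 10.8 mandatory and add B vs C.
- State which PFS definition was used for the 95-event count and the 126-event prediction.
- Align 10.1 with 10.3. Read alone, 10.1 would also censor a subject who progressed before the new therapy; 10.3 shows that such events count.
- Separately, reconcile Table 8 footnotes h and i and the Tumor Assessments Schedule in Protocol 5.3.1.1 on imaging when clinical progression is suspected.

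The cost is SAP wording and a few extra tables. The analysis uses scans and deaths that the Protocol already plans to collect, as far as subjects remain in follow-up.
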